8.3.1 Adverse Events

An adverse event (AE) is any untoward medical occurrence in a subject participating in a clinical trial. An AE can be any unfavorable and unintended sign, symptom, or disease temporally associated with the use of the study medication, whether or not considered related to the study medication. AEs will be collected from the start of treatment until 30 days following the final visit dose. If the subject enters the extension study, the first 30 days of the extension study will be considered the observation period for adverse events of this study (PB-102-F50). Any events occurring prior to treatment will be recorded on the medical history page with the event name and onset date and end date if not continuing. Known pre-existing clinically significant conditions observed at screening should be recorded as medical history.

This definition also includes accidental injuries, reasons for any change in medication (drug and/or dose) other than planned titration, reasons for admission to a hospital, or reasons for surgical procedures (unless for minor elective surgery for a pre-existing condition). It also includes AEs commonly observed and AEs anticipated based on the pharmacological effect of the study medication. Any laboratory abnormality assessed as clinically significant by the Investigator must be recorded as an AE.

A treatment-emergent AE is any AE occurring after start of study medication and within the time of residual drug effect (30 days after the last administration of the study medication; please note the above provision for subjects who enter the extension study), or a pre-treatment AE or pre-existing medical condition that worsens in intensity after start of study medication and within the time of residual drug effect.

AEs should be recorded as diagnoses, if available. If not, separate sign(s) and symptom(s) are recorded. One diagnosis/symptom should be entered per record. Treatment-related hypersensitivity/infusion reactions are defined in [Appendix 3. Pegunigalsidase alfa Hypersensitivity Evaluation and Treatment Algorithm](#) and can be defined as a single AE at the Investigator's discretion.

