10.3.2 Safety Analysis

10.3.2.1 Adverse Events

Adverse events (AE) will be coded to system organ class and preferred term using MedDRA version 9.1 or higher. All AEs occurring after the initiation of the study treatment (treatment-emergent AEs) will be reported, including events present at baseline that worsened during the study.

AEs will be summarized by treatment group to provide visual comparison among the treatment groups with respect to incidence of AEs (the number of subjects reporting at least one episode of a specific AE), incidence of AEs by severity within body system, incidence of AEs by attribution within body system, and incidence of AEs causing withdrawal and incidence of SAEs. Regarding severity and attribution summaries, the most extreme outcome (highest severity and closest to study drug related) will be used for those subjects who experience the same AE on more than one occasion.

Hypersensitivity reactions will be analyzed as AEs of special interest using descriptive statistics.

Written narratives will be provided for all serious, unexpected or other significant AEs that are judged to be of special interest because of their clinical importance.

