## 2. INTRODUCTION

The statistical analysis plan (SAP) contains the analysis information in detail on the definition of the analysis populations, derivation of variables, convention of analysis scope, and statistical methodology for the analyses of safety and efficacy of pegunigalsidase-alfa (PRX-102) 2mg/kg administered every 4 weeks based on data collected per protocol PB-102-F50. Should the SAP and the protocol be inconsistent with respect to the planned analyses, the language of the SAP is governing. Any deviations from this SAP during the actual data analysis will be documented properly in a change request or a note-to-file document, as well as in the Clinical Study Report (CSR). The SAP will be finalized before the first database lock (DBL).

Analysis of PK endpoints will be presented in a separate document.

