### 10.2 Adverse Events

#### 10.2.1 AE Overall

Adverse events (AE) will be coded by the Medical Dictionary for Drug Regulatory Activities (MedDRA) version 19.0 or higher.

Pre-treatment AEs include all AEs collected prior to the first pegunigalsidase alfa infusion. Pre-treatment AE will only be listed.

Treatment-emergent adverse event (TEAE) is any AE occurring after the start of the first infusion of pegunigalsidase alfa. In case the date of onset is completely unknown,

the AE will be classified as TEAE. In case the date is partially known and the month is earlier than the month of first infusion, the event will be classified as pre-treatment AE.

The number and percentage of patients with at least one TEAE and the number of TEAEs will be reported in an overall table for the following parameters: Any TEAE; Related (possibly, probably or definitely related) TEAEs; Mild or moderate TEAEs; Related mild or moderate TEAEs; Severe TEAEs; Related severe TEAEs; Serious TEAEs; Non-serious TEAEs; Related serious TEAEs; TEAEs leading to withdrawal; Related TEAEs leading to withdrawal; TEAEs leading to death; and related TEAEs leading to death.

In the analysis by severity, subjects whose event was classified as “Very Severe” or “Fatal” will be presented in the “Severe” category.

This analysis will be repeated for the following sub-groups: ADA; Gender; Previous ERT; FD classification.

This overall analysis will be repeated for injection site reaction TEAEs.

TEAE summary tables by the MedDRA System Organ Class (SOC) and Preferred Term (PT) will present the number and percentage of subjects with at least one TEAE and the number of TEAEs. These tables will be generated overall; by severity; and by relationship to study drug.

Similar tables by SOC and PT will be generated for serious TEAEs overall and by relationship to study drug.

In the summaries of severity and relationship to study drug, the most extreme outcome (highest severity and closest relationship to study drug) will be used for those subjects who experience the same TEAE (per PT) more than once.

Missing values associated with TEAEs will be treated as missing except for causality, intensity, and outcome of a TEAE: for these variables a “worst case” approach will be taken in the analysis. Thus:

- If the causality is missing, the TEAE will be regarded as related to pegunigalsidase alfa.

- If the intensity is missing, the intensity of the AE will be regarded as severe.

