## **12. DIFFERENCES FROM PROTOCOL**

The statistical section of the protocol is short and was not meant to provide detailed information for the analysis. Some of the changes in the planned analysis of PB-102-F50 are due to knowledge and insights gained in the overall clinical program of PRX-102.

The main changes in the analysis plan compared to protocol are as follows:

1. The following endpoints were added: Infusion Related Reaction (IRR) and Fabry clinical events.
2. Analysis sets: the protocol defined the Intent-to-Treat as the main efficacy set. The SAP revised the main efficacy set to be called Efficacy population. It differs from the Intent-to-Treat proposed in the protocol that requires that a patient should have at least one post

baseline observation. The Per-Protocol set was removed since there is no primary endpoint and no sensitivity analysis is planned.

3. Efficacy variables: the protocol specified that the percent change from baseline will be used for quantitative efficacy endpoints. The SAP revised this, and depending on the endpoint, either a change from baseline or percent change from baseline or both are being used. For some of the efficacy end-point, only a shift table is presented.
4. Descriptive statistics for all variables include: mean (SE), SD, median, minimum and maximum. The interquartile range is not presented.
5. No shift tables are used for safety variables.
6. Evaluation of Acute Kidney Injuries is based on AE reporting and clinical judgment of the investigator and not by independent nephrologists.
7. 95% CI; Shift tables were added for some efficacy.
8. The statistical section of the protocol stated that hypersensitivity will be analysed as AE of special interest. Since IRR is a wider analysis which was added (see item 1 in this list), then the analysis of hypersensitivity will be part of the IRR evaluation.

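### SAP 10.2.1 defines treatment-emergent events by onset alone and drops the protocol's worsening clause without declaring it

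*SAP*

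**What the plan says.** **Protocol.** Section 8.3.1 gives two ways for an event to be treatment-emergent. It may start after study medication begins, or it may be "a pre-treatment AE or pre-existing medical condition that worsens in intensity after start of study medication". Both are bounded by 30 days after the last administration. Section 10.3.2.1 repeats the second route for the analysis: TEAEs are reported "including events present at baseline that worsened during the study".

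**SAP.** Section 10.2.1 says that a TEAE "is any AE occurring after the start of the first infusion of pegunigalsidase alfa". The sentences that follow sort by date of onset: a wholly unknown onset makes the event a TEAE, and a partial date in a month before that of the first infusion makes it pre-treatment. The pre-treatment class is broad: "Pre-treatment AEs include all AEs collected prior to the first pegunigalsidase alfa infusion". Its handling is equally plain: "Pre-treatment AE will only be listed". Listing 16.3.2.1 is reserved for these events.

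**Precedence and declaration.** SAP Section 2 states: "Should the SAP and the protocol be inconsistent with respect to the planned analyses, the language of the SAP is governing". Section 12 opens its list with "The main changes in the analysis plan compared to protocol are as follows". The list has eight items, and none concerns the TEAE definition.

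**Data capture.** Protocol 8.3.1 collects AEs from the start of treatment. For earlier events it says: "Any events occurring prior to treatment will be recorded on the medical history page with the event name and onset date". Neither document says how a later worsening of such an event is entered.

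**The concern.** The study is justified in both documents as adequate to evaluate the safety of switching, and TEAEs head the list of safety endpoints in SAP 3.2.1. Every patient enters with at least one characteristic Fabry feature, and the protocol foresees that some may deteriorate after the switch. Worsening of something already present is therefore a foreseeable safety finding, and the protocol took care to count it.

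The SAP definition sits under every TEAE table. It also sits under the infusion-related reaction (IRR) tables, because SAP 10.2.2 defines IRRs as a subset of TEAEs. A programmer who follows the governing document would test onset and never look at later intensity. This runs against the SAP's own conservative rules in the same section, where missing causality is taken as related and missing intensity as severe. A further view of worsening is also gone: Section 12 drops shift tables for safety variables, which removes the laboratory shifts planned in protocol 10.3.2.2.

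**Working it through.** There is no plan figure to reproduce. The check sets the two definitions side by side and follows a worsening event through each way it could be recorded.

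| Element | Protocol 8.3.1 and 10.3.2.1 | SAP 10.2.1 |
|---|---|---|
| New onset after first infusion | TEAE | TEAE |
| Present before, worsens after | TEAE | No provision; sorted by onset |
| AE with onset before first infusion | TEAE if it worsens | Pre-treatment, listed only |
| Upper limit | 30 days after last administration, for both routes | None stated |

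**Routes for a worsening event**

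1. The condition is on the medical history page and the worsening is entered as a new AE with a post-infusion onset. It is a TEAE under both documents. Difference: none.
2. An AE record starts before the first infusion and the worsening is entered as a second AE record with a post-infusion onset. The worsening is a TEAE under both. Difference: none.
3. An AE record starts before the first infusion and the worsening is shown only by a higher intensity in that same record. The protocol makes it a TEAE. The SAP makes it pre-treatment and lists it. Difference: one event lost from the tables, and one patient lost from any row in which that patient has no other qualifying event.

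Only route 3 separates the documents, and there the SAP always gives the lower count. No event becomes a TEAE because the worsening clause is absent. An event lost by route 3 cannot be an IRR either, since an IRR must first be a TEAE.

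**Scale.** The number of patients is 30 (SAP 4.1). If k patients are lost from a row, the incidence falls by k/30. The documents do not give k, so these values are assumptions:

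- k = 0: 0 points
- k = 1: 1/30 = 3.3 percentage points
- k = 2: 2/30 = 6.7 percentage points
- k = 3: 3/30 = 10.0 percentage points

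**A second difference.** The SAP definition also lacks the protocol's 30-day upper limit, and Section 12 does not mention this. That difference can only add events. The statement on direction therefore applies to the worsening clause taken alone, not to the two differences together.

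**The case against.** The strongest reply is that the protocol's data-capture rules leave little for the omission to act on. AEs are collected only from the start of treatment, the flow charts in both documents show no AE assessment at screening, and anything earlier belongs on the medical history page. As 8.3.1 describes it, that page holds name and dates but no intensity. A worsening on drug fits the protocol's general definition of an AE, so it would most naturally be entered as a new AE with a post-infusion onset, and the SAP would then count it.

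This disposes of a stronger reading that a reader might infer: that chronic Fabry symptoms which worsen after the switch disappear from all TEAE tables. The documents do not support it. Such symptoms are medical history, not pre-treatment AE records, so the listing-only rule does not reach them.

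The reply does not remove the point. The natural recording route is nowhere made a rule. The SAP also defines a pre-treatment AE class and reserves a listing for it, so it provides for AE records with onset before the first infusion.

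Two further replies carry less weight. Section 12 claims only to give the main changes, but a narrower definition behind every TEAE table belongs among them. Worsening may also show in the Brief Pain Inventory, the Mainz score, pain medication shifts, eGFR slope and Fabry clinical events. These are exploratory efficacy analyses, and they do not replace TEAE tables by causality, seriousness and withdrawal.

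**Conclusion.** The conflict in the text is real and undeclared. The governing SAP definition omits a route to TEAE status that the protocol states twice. Taken alone, this can only lower TEAE and IRR counts.

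The consequence is limited to AE records that start before the first infusion and worsen afterwards without a new record. It is nil if sites enter every worsening as a new AE with a post-infusion onset. If they do not, each affected patient is worth up to 3.3 percentage points in a row, and only where no other event already puts that patient in it. The number of such patients cannot be derived from the documents and may well be zero.

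The conclusion reads occurrence in SAP 10.2.1 as onset, which the date rules in that section support. It also assumes that SAP 7.1, whose text was not available, contains no worsening rule.

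**What to change.** In SAP 10.2.1:

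- Restore the protocol 8.3.1 definition, so that a TEAE also includes an AE or condition present before the first infusion whose intensity increases after it.
- If the 30-day limit after the last dose is used, apply it equally to new-onset and worsened events, as the protocol does, with its provision for patients who enter the extension. Attaching it to worsened events alone would create a new mismatch.
- State how worsening is identified: by a new AE record, or by an increase in recorded intensity after the first infusion.
- Restrict listing-only treatment to pre-treatment AEs that do not worsen.

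If the narrowing is intended, add it to Section 12 with a reason. If sites were already told to enter every worsening as a new AE, one sentence saying so settles the matter of counts.

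If the SAP is already final, Section 2 gives the route: a change request or note-to-file, and a statement in the study report. The cost is a few lines of text, a small amount of extra programming, and possibly slightly higher TEAE counts. No new data collection is needed. Label: cheap improvement.

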6.3.3 Removal of Subjects from Therapy or Assessment

Reasons for permanent discontinuation include the following:

- The subject experiences two or more Grade 3 toxicities or one or more Grade 4 toxicity considered by the Investigator to be associated with pegunigalsidase alfa ([CTCAE v. 4.03, 2010](#))
- The subject experiences progressive hypersensitivity or severe hypersensitivity that is not allayed with pre-treatment

- The subject requests to discontinue treatment
- Investigator feels that it is not in the best interest of the subject to continue treatment and/or if the Investigator believes that the subject can no longer be compliant with the requirements of the study

For any discontinuation, the Investigator will obtain all the required details and document the date and the main reason for the premature termination. If the reason for discontinuation is an adverse event, the specific event or the main laboratory abnormality will be recorded in the CRF. The Investigator will make thorough efforts to document the outcome. The Investigator will attempt to continue to follow the subject for the full duration of the study or at least for 30 days following discontinuation. If circumstances prevent the subject from completing all visits, every attempt will be made to complete all procedures listed in [Section 9.2.3](#) for Visit 14 excluding the drug infusion.

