8.3.1.1 Procedures for Assessing, Recording, and Reporting AEs and SAEs

Throughout the duration of the study, the Investigator will closely monitor each subject for evidence of drug intolerance and for the development of clinical or laboratory evidence of AEs. All AEs (expected or unexpected) which occur during the course of the study, whether observed by the Investigator or by the subject, and whether or not thought to be drug-related, will be reported and followed until resolution or until they become stable.

The description of the AE will include description of the event, start date, stop date, intensity, if it was serious, relationship to test drug, change in test drug dosage, if the subject died, and if treatment was required.

AEs with the causality assessed as possible or probable are categorized as related to study medication and are called adverse drug reactions.

All SAEs must be reported immediately (no more than 24 hours after becoming aware of the event) by entering the information about the event in the eCRF forms. The Sponsor's Medical Director and Safety Monitor will be notified of the event by the eCRF system. In the case that the eCRF system is not available, the Investigator must contact Medical Director ([name]) or Safety Monitor (1-([contact]) to notify the Sponsor of the event.

Events will be recorded as one of the following severity and causality categories below:

| Severity | Definition |
|-----------------------|--|
| Mild (Grade 1) | Awareness of signs or symptoms, but no disruption of usual activity |
| Moderate (Grade 2) | Discomfort sufficient to interfere, but not prevent, daily activity |
| Severe (Grade 3) | Unable to carry out usual activity |
| Very severe (Grade 4) | Incapacitating, requires hospitalization, results in death |
| Category | Definition |
| Unrelated | Clearly and incontrovertibly due only to extraneous causes, and does not meet criteria listed under possible or probable. |
| Unlikely | Does not follow a reasonable temporal sequence from administration. May have been produced by the subject's clinical state or by environmental factors or other therapies administered. |
| Possible | Follows a reasonable temporal sequence from administration, but may have been also produced by the subject's clinical state, environmental factors or other therapies administered. |

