**Table 2: Injection Site Reaction SOC and PT Not Considered as IRR**

MedDRA SOC	MedDRA Preferred Term
General disorders and administration site conditions	Infusion site discomfort Injection site discomfort Infusion site pain Injection site pain Infusion site hematoma Injection site hematoma
Injury poisoning and procedural complications	Contusion Procedural site reaction Procedural pain
Vascular disorders	Vein rupture

The number and percentage of patients with at least one IRR and the number of IRRs will be reported in an overall table with the following parameters: Any IRR; Mild or moderate IRRs; Severe IRRs; Serious IRRs; IRRs leading to withdrawal; IRRs leading to death.

This analysis will be repeated for the following sub-groups: ADA; Gender; Previous ERT; FD classification. An additional sub-group will be the location of administration (Home or Site).

IRR summary tables by SOC and PT will present the number and percentage of subjects with at least one IRR and the number of IRRs. The tables for the IRRs will be presented overall and by severity.

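### The SAP counts very severe, fatal and missing-intensity events as Severe, so no planned severity table can count patients with a non-fatal Grade 4 event

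*SAP*

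**What the plan says.** Protocol Section 8.3.1.1 has the investigator record severity as mild, moderate, severe or very severe (Grades 1 to 4). The top grade is defined as "Incapacitating, requires hospitalization, results in death". Death therefore sits inside Grade 4, and the scale has no separate fatal level. Protocol Section 10.3.2.1 plans incidence by severity, taking each patient's worst grade, and mentions no merging of grades.

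SAP Section 10.2.1 changes this in two sentences. First, "subjects whose event was classified as “Very Severe” or “Fatal” will be presented in the “Severe” category". Second, "If the intensity is missing, the intensity of the AE will be regarded as severe". The same section treats missing causality as related to study drug. Its overall TEAE table has only two severity bands, one for mild or moderate and one for severe, each shown for all events and for related events. The table by system organ class and preferred term (14.3.3.3.2) can go no higher than Severe.

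For infusion-related reactions, SAP Section 10.2.2 lists these rows: "Any IRR; Mild or moderate IRRs; Severe IRRs; Serious IRRs; IRRs leading to withdrawal; IRRs leading to death". It does not restate the merge, but it offers no row above Severe.

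SAP Section 12, which lists the main differences from the protocol, does not mention the merge. SAP Section 2 says the SAP governs where the two documents differ.

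**The concern.** The study's size is justified only as adequate to assess the safety of switching (Protocol Section 10.1, SAP Section 4.1). Safety tables are therefore its main product, and the most severe reactions are the ones a reader will look for first. The plan collects the grade that identifies them and then removes it from every severity summary.

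Infusion reactions add to the concern. SAP Section 12 (item 8) moves the protocol's separate hypersensitivity analysis into the IRR evaluation, so the IRR rows become the main severity summary for hypersensitivity. The grade of such a reaction has mattered in this programme: Protocol Section 4 reports a Grade 3 hypersensitivity-related bronchospasm that led to discontinuation.

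At stake is whether a reader can learn from the tables how many patients had a very severe, non-fatal event, and whether a Severe count reflects recorded grades or the missing-data rule.

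**Working it through.** The plan gives no figure to reproduce. The check takes each possible severity entry through the SAP rules to the planned tables.

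**Inputs.** The four protocol grades (Protocol 8.3.1.1); the Fatal entry and the missing-intensity rule (SAP 10.2.1); the table rows (SAP 10.2.1, 10.2.2, 13.1); 30 patients (SAP 4.1). The table shells are in a separate document, so I assume the SOC/PT table keeps mild and moderate apart.

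**Step 1: mapping.**

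| Entry | Overall TEAE table | SOC/PT severity table |
|---|---|---|
| Mild | Mild or moderate | Mild |
| Moderate | Mild or moderate | Moderate |
| Severe (Grade 3) | Severe | Severe |
| Very severe (Grade 4) | Severe | Severe |
| Fatal | Severe | Severe |
| Missing | Severe | Severe |

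Six entries become two bands in the overall table and three levels in the SOC/PT table. Four of the six fall into Severe.

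**Step 2: can other rows recover the grade?** The overall TEAE table has 13 parameters. Take three patients with one event each, all serious, none fatal, none leading to withdrawal:

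- A: related, Grade 3, serious because of hospitalisation.
- B: related, Grade 4.
- C: intensity and causality both missing, so counted as severe and related.

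Each adds 1 to six rows (any, related, severe, related severe, serious, related serious) and 0 to the other seven. The three patients look the same in all 13 rows. Each is 1/30 = 3.3% of the Related severe row if all 30 are in the safety set.

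**Step 3: how tightly do the serious rows bound the count?** The serious tables (14.3.3.4.1 and 14.3.3.4.2) are split by relationship, not by severity. Suppose the overall table shows 2 patients severe, 2 serious and no deaths. Even if every Grade 4 event is serious, the number of patients with a non-fatal Grade 4 event could be anything from 0 to min(2, 2) = 2, that is 0% to 2/30 = 6.7%. The rows give an upper limit but not the count.

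**Step 4: deaths.** The overall TEAE table and the IRR summary both have rows for events leading to death. Fatal events can therefore be counted, and the loss concerns non-fatal Grade 4 events and imputed entries.

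**The case against.** The case for leaving the tables alone has several parts.

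- *Deaths and withdrawals are visible.* Both have their own rows, such cases are presented by patient (SAP 10.2.1), and there is a dedicated listing (16.3.2.3). This stands. It does not reach a Grade 4 event in a patient who stayed on treatment. An event judged unrelated is an example, since the toxicity criterion in Protocol Section 6.3.3 covers only toxicities attributed to study drug.
- *Grade 4 events will mostly be serious.* The protocol's Grade 4 definition overlaps heavily with its seriousness criteria, and Protocol Section 10.3.2.1 promises narratives for serious events. This largely stands, and it caps the number. It does not give the number, because a Grade 3 event can also be serious.
- *Nothing is lost from the data.* SAP Section 13.3 says the listings show all collected data, so recorded grades should appear in Listing 16.3.2.2, although severity is not named as a column. This stands and confines the point to the summary tables.
- *Counting missing intensity as severe is conservative.* It is, and nothing in the documents suggests it will be used often. The unpublished shells may already flag imputed values. The SAP text does not require it.
- *Use of the merge for IRRs is inferred.* This is correct. The sentence is in Section 10.2.1 only; the inference rests on the rows in Section 10.2.2.
- *The study is descriptive.* No tests are planned (SAP 7.4), so no inference is affected. For the same reason, sparse cells are a weak argument for merging.

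**Conclusion.** The point holds as a minor reporting matter. A stated SAP rule discards a severity level that the protocol collects, and Section 12 does not record it. No planned TEAE severity table can give the number of patients with a non-fatal Grade 4 event or the number of Severe entries that were imputed. The same is true of the IRR tables if the merge is applied there. How many patients this affects cannot be known from the documents; each one is 3.3% of a row if all 30 are in the safety set.

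A reader might go further and infer that Grade 4 events alone trigger permanent discontinuation, so that the merge hides whether the stopping rule was followed. The documents do not support that:

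- Protocol Section 6.3.3 names "two or more Grade 3 toxicities or one or more Grade 4 toxicity considered by the Investigator to be associated with pegunigalsidase alfa". One related Grade 4 toxicity is enough, but so are two related Grade 3 toxicities.
- The same section lists other reasons, including this one: "The subject experiences progressive hypersensitivity or severe hypersensitivity that is not allayed with pre-treatment". Patient request and investigator judgement are there as well.
- The rule cites CTCAE v4.03, whereas events are recorded on the protocol's own four-grade scale, and the documents do not equate the two. A separate Grade 4 row would therefore not in itself verify the rule.

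**What to change.** 1. In Tables 14.3.3.1.x and 14.3.3.3.2, show Severe (Grade 3) and Very severe (Grade 4) separately. Do the same in IRR Tables 14.3.3.5.x and 14.3.3.6.2 if the merge is meant to apply there, and state in SAP Section 10.2.2 whether it does.
2. Keep fatal events identifiable through the existing death rows, and footnote whether the Grade 4 row includes them.
3. Footnote in each table the number of events whose intensity was imputed. Once the grades are split, the SAP must also say which row receives them.
4. If the merge is kept, list it in SAP Section 12.
5. Reconcile the severity scale in Protocol Section 8.3.1.1 with the CTCAE grades cited in Section 6.3.3, so that a reader knows how a tabulated grade relates to the discontinuation criterion. This is a request for consistency and does not question the criterion.

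The grades are already collected. The overall TEAE table gains two rows (all and related very severe events), the other tables gain one row or level, and each gains a footnote. The drawback is sparse cells, which matter little where no tests are planned.
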